1. PROTOCOL SUMMARY

1.1. Synopsis

Not applicable.

1.2. Schema

Not applicable.

1.3. Schedule of Activities

The SoA table provides an overview of the protocol visits and procedures. Refer to the **STUDY ASSESSMENTS AND PROCEDURES** section of the protocol for detailed information on each procedure and assessment required for compliance with the protocol.

The investigator may schedule visits (unplanned visits) in addition to those listed in the SoA table, in order to conduct evaluations or assessments required to protect the well-being of the participant.

Visit Identifier	Screening	Period 1 (P1) and Period 2 (P2), unless otherwise limited to 1 of these 2 Periods ^a																				F/U Phone Call	ET			
Days Relative to Day 1	-42 to -2	-1	1												2		3^b		4	5	6	7-21^c	≥28 - 35 days	-		
Hours After Oral PF-06865571 Dose	-	-	0	0.5	1	2	3	3.08	3.17	3.25	3.5	3.75	4	6	9	12	16	24	27	36	48	51	72	96	120	
Hours After IV [¹⁴C]PF-06865571 Dose (P2 Only)			-3				0	0.08	0.17	0.25	0.5	0.75	1	3	6	9	13	21	24	33	45	48				
Informed Consent	X																									
Inclusion/Exclusion Criteria	X	X																								
Admission to the CRU (P1 only)		X																								
CRU confinement		X	→	→	→	→	→	→	→	→	→	→	→	→	→	→	→	→	→	→	X ^{b,c}	→	→	→	X ^c	
Medical/medication history (update)	X	X																								
Height and Weight	X																				X ^c					X
Physical Examination ^d		X																								
Supine 12-lead ECG	X		X																		X ^c					X
Supine Vital Signs (Blood Pressure and Pulse Rate)	X		X																		X ^c					X
COVID-19 questionnaire ^f	X	X																								

PFIZER CONFIDENTIAL

Visit Identifier	Screening	Period 1 (P1) and Period 2 (P2), unless otherwise limited to 1 of these 2 Periods ^a																					F/U Phone Call	ET				
Days Relative to Day 1	-42 to -2	-1	1												2			3 ^b			4	5	6	7-21 ^c	≥28 - 35 days (P2 only)	-		
Hours After Oral PF-06865571 Dose	-	-	0	0.5	1	2	3	3.08	3.17	3.25	3.5	3.75	4	6	9	12	16	24	27	36	48	51	72	96	120	-		
Hours After IV [¹⁴ C]PF-06865571 Dose (P2 Only)			-3				0	0.08	0.17	0.25	0.5	0.75	1	3	6	9	13	21	24	33	45	48						
COVID-19 temperature check ^g	X	X	X ^h	→	→	→	→	→	→	→	→	→	→	→	→	→	→	→	→	→	→	→	→	→	X		X	
Serious and Non-serious Adverse Event Monitoring	X	→	→	→	→	→	→	→	→	→	→	→	→	→	→	→	→	→	→	→	→	→	→	→	X	X	X	
Standard Meals ⁱ		X	X ⁱ												X	X		X	X	X	X	X	X	X				
Oral 300 mg [¹⁴ C]PF-06865571 Administration (P1 Only)			X																									
Oral 300 mg PF-06865571 Administration (P2 only)			X																									
IV infusion 100 µg [¹⁴ C]PF-06865571 Administration (P2 Only)							X	→	→	X																		
COVID-19 testing ^k	X	X																						X		X ^k		
Emesis Collection for Radioactivity Measurement, if Occurs (P1 Only)			X	→	→	→	→	→	→	→	→	→	→	→	→	→	→	→	→	→	→	→	X					

PFIZER CONFIDENTIAL

Visit Identifier	Screening	Period 1 (P1) and Period 2 (P2), unless otherwise limited to 1 of these 2 Periods ^a																						F/U Phone Call	ET			
Days Relative to Day 1	-42 to -2	-1	1												2		3 ^b			4	5	6	7-21 ^c	≥28 - 35 days (P2 only)	-			
Hours After Oral PF-06865571 Dose	-	-	0	0.5	1	2	3	3.08	3.17	3.25	3.5	3.75	4	6	9	12	16	24	27	36	48	51	72	96	120	-		
Hours After IV [¹⁴ C]PF-06865571 Dose (P2 Only)			-3				0	0.08	0.17	0.25	0.5	0.75	1	3	6	9	13	21	24	33	45	48						
Blood Sample Collection for -																												
PK of PF-06865571 following oral [¹⁴ C]PF-06865571 in P1 and unlabeled PF-06865571 in P2 ^d			X	X	X	X	X							X	X	X	X	X	X	X	X	X	X	X	X	X	X	
Total Radioactivity ^m (P1 only)	X		X	X	X	X	X							X	X	X	X	X	X	X	X	X	X	X	X	X	X	
Metabolite profiling/ID ^m (P1 only)			X	X			X							X		X		X		X	X		X	X	X	X	X	
PK of IV infusion [¹⁴ C]PF-06865571 (P2 Only)			X ⁿ			X	X	X	X	X	X	X	X	X	X	X	X	X	X	X								
Safety laboratory	X	X																			X ^e						X	
HIV, HBsAg, HCVAb	X																											
Pfizer Genomic Prep D1.5 Banked Biospecimen (P1 Only) ^o			X																									
Pfizer Prep B1 Banked Biospecimen (P1 Only) ^o			X																									

PFIZER CONFIDENTIAL

Visit Identifier	Screening	Period 1 (P1) and Period 2 (P2), unless otherwise limited to 1 of these 2 Periods ^a																						F/U Phone Call	ET		
Days Relative to Day 1	-42 to -2	-1	1												2		3 ^b		4	5	6	7-21 ^c	≥28 - 35 days	-			
Hours After Oral PF-06865571 Dose	-	-	0	0.5	1	2	3	3.08	3.17	3.25	3.5	3.75	4	6	9	12	16	24	27	36	48	51	72	96	120	144-504	
Hours After IV [¹⁴ C]PF-06865571 Dose (P2 Only)			-3				0	0.08	0.17 (10 min)	0.25 (15 min)	0.5 (30 min)	0.75 (45 min)	1	3	6	9	13	21	24	33	45	48				(P2 only)	
Urine Sample collection for -																											
Spot Collection for Urine Drug Screening (P1 only)	X	X																									
Spot Collection for Urine Cotinine Screening (P1 only)	X	X																									
Spot Collection for Urinalysis (and Microscopy, if needed) ^d	X	X																								X	
Total Radioactivity and Metabolite profiling/ID ^q (P1 Only)		X ^q	X	→	→	→	→	→	→	→	→	→	→	→	→	→	X	→	X	→	→	X	→	X	X	X	X
Total Radioactivity ^q (P2 Only)							X	→	→	→	→	→	→	→	→	→	X	→	→	X	→	→	X ^q				
Feces Sample collection for -																											
Total Radioactivity and Metabolite ID ^r (P1 Only)		X ^r	X	→	→	→	→	→	→	→	→	→	→	→	→	→	→	X	→	→	X	→	X	X	X	X ^r	X
[¹⁴ C]PF-06865571 ^r (P2 Only)							X ^r	→	→	→	→	→	→	→	→	→	→	→	→	→	→	X	→	→	X ^r		

Abbreviations: →= ongoing/continuous event; AE = adverse event; COVID-19 = Coronavirus disease 2019; CRU = Clinical Research Unit; ECG = electrocardiogram; ET=early termination; F/U=follow-up; HCVAb = hepatitis C antibody; HBsAg = hepatitis B surface antigen; HIV = human immunodeficiency virus; P1 = Period 1; P2 = Period 2; PK = pharmacokinetics; SAE = serious adverse event; LC/MS = liquid chromatography tandem mass spectrometry; ET = early termination.

Visit Identifier	Screening	Period 1 (P1) and Period 2 (P2), unless otherwise limited to 1 of these 2 Periods ^a																					F/U Phone Call	ET	
Days Relative to Day 1	-42 to -2	-1																							
Hours After Oral PF-06865571 Dose	-	-	0	0.5	1	2	3	3.08	3.17	3.25	3.5	3.75	4	6	9	12	16	24	27	36	48	51	72	96	120
Hours After IV [¹⁴ C]PF-06865571 Dose (P2 Only)			-3				0	0.08 3 (5 min)	0.17 (10 min)	0.25 (15 min)	0.5 (30 min)	0.75 (45 min)	1	3	6	9	13	21	24	33	45	48			

Note: Black color denotes oral dose administration and sampling post oral administration and Red color denotes IV dose administration and sampling post IV administration. IV samples may optionally be labeled with the corresponding time relative to the oral dose for sample collection; however, PK data for the IV administration will be analyzed relative to the start of the IV infusion.

- There will be a wash-out period of 8-22 days from drug administration in Period 1 and Period 2. The day to start Period 2 is dependent on the duration for Period 1 but will be at least after all sample collection in Period 1 are complete.
- In Period 2, participants will be discharged on Day 3 (ie, 48 hours IV dose administration).
- Dosing in Period 2 (as 1 cohort) or Completion of Period 1 (1 participant at a time) when at least 1 of 3 criteria are met: (1) ≥90% of radioactive dose has been recovered in urine+feces+emesis (if any); (2) <1% of radioactive dose has been recovered in urine+feces during 24H interval over 2 consecutive days; (3) participant has reached Day 21 (in Period 1). At the latest, Period 2, Day -1 would occur on the same day as Period 1, Day 21.
- Full physical examination will be conducted at Day -1 (Period 1); otherwise brief physical exam envisioned for findings during previous PE or new/open AEs, at Investigator discretion.
- Procedures to be completed at time of discharge in Period 2 only.
- A site-generated questionnaire checking suspected contact and COVID-19 related symptoms to be completed by participants.
- Participant's body temperature will be checked at least twice daily (approximately 12 hours apart) during the CRU confinement.
- The first body temperature check on Day 1 of each period will be performed before PF-06865571 dosing.
- Standardized meals to be served at clock times matching approximately **-0.5H** (see Section 5.3.1), and at 4H and 9-10H relative to oral PF-06865571 dosing.
- Testing for COVID-19 pathogen (SARS-CoV-2) by PCR will be performed at each visit to the CRU (Screening and Admission). For participants admitted for residence in the CRU, subsequent COVID-19 tests will be performed 2x/week at a minimum.
- For Period 2, Plasma PK of PF-06865571 will only be assessed up to 48 hours.
- Samples are to be collected up to 120 hours. Based on emerging data, up to 2 additional samples for total ¹⁴C accelerator mass spectrometry (AMS) and metabolite profiling between Day 7 and Day 21 of Period 1 completion may be collected.
- Sample will be used for sample dilution, if necessary, using matrix matched plasma. [¹⁴C]PF 06865571 concentration will not be determined in this sample.
- If not collected on the designated collection day, the banked biospecimen can be collected at the next available time point when biospecimens are being collected in conjunction with a participant visit.

PFIZER CONFIDENTIAL

Visit Identifier	Screening	Period 1 (P1) and Period 2 (P2), unless otherwise limited to 1 of these 2 Periods ^a																					F/U Phone Call	ET	
Days Relative to Day 1	-42 to -2	-1																							
Hours After Oral PF-06865571 Dose	-	-	0	0.5	1	2	3	3.08	3.17	3.25	3.5	3.75	4	6	9	12	16	24	27	36	48	51	72	96	120
Hours After IV [¹⁴ C]PF-06865571 Dose (P2 Only)			-3				0	0.08 3 (5 min)	0.17 (10 min)	0.25 (15 min)	0.5 (30 min)	0.75 (45 min)	1	3	6	9	13	21	24	33	45	48			

p. Microscopy required only if urine dipstick is positive for blood, protein, nitrites, or leukocyte esterase.

q. “Blank” sample collected within 24H prior to dosing in each period; and over intervals of 0-12H, 12-24H, 24-48H, 48-72H, 72-96H, 96-120H plus each 24H interval, relative to *oral* dosing in Period 1. In Period 2, samples will be collected over 0-12H, 12-24H and 24-48H following administration of *IV* radiolabeled drug.

r. “Blank” sample collected within 24H prior to dosing in each period; samples collected over 0-24H, 24-48H, 48-72H, 72-96H, 96-120H plus each 24H interval relative to *oral* dosing in Period 1. In Period 2, samples will be collected over 0-24H and 24-48H following administration of *IV* radiolabeled drug.

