2.2.2.2. Summary of Clinical Pharmacology

Following administration of single oral doses of PF-06865571 under fed conditions in C2541001, median time for C_{max} (T_{max}) ranged from 1.5 to 4 hours across the dose groups. Approximate dose-proportional increases in C_{max} and AUC_{24} were observed between the 5 mg and 1500 mg doses. Under fed conditions, the mean terminal elimination half-life ($t_{1/2}$) ranged from 1.5 to 5.2 hours. At the 1000 mg dose level, exposures under fasted condition were approximately 2-fold lower than those in the fed state. Median PF-06865571 T_{max} occurred earlier in the fasted state, compared to dosing under fed conditions (1 h versus 4 h). In addition, the terminal elimination $t_{1/2}$ under fasted conditions was more variable than under fed conditions.

Following repeated administration of oral doses of PF-06865571 under fed conditions in C2541002, C_{max} values on Days 1, 7 and 14 were observed within a median T_{max} range of 1.5 to 3.0 hours post-dose across the 30 mg - 600 mg Q8H doses. Steady state appeared to have been reached by Day 4 based on PF-06865571 median trough plasma concentration-time profiles. Following a single dose on Day 1 and at steady state (Days 7 and 14), PF-06865571 plasma exposure across the 30 mg - 600 mg Q8H doses appeared to increase in a dose proportional manner based on geometric mean AUC_{tau} and C_{max} values. Mean $t_{1/2}$ on Day 14 ranged from 3.29 hours to 6.92 hours across the 30 mg - 600 mg Q8H doses with longer $t_{1/2}$ values observed at higher doses. Minimum drug accumulation was observed following multiple dose administration of PF-06865571 Q8H. Mean accumulation ratios ranged from 0.950 to 1.33 based on AUC_{tau} values and 0.990 to 1.44 based on C_{max} values across all doses on both Day 7 and Day 14. The proportion of drug excreted via renal elimination on Day 14 was low, with less than approximately 2% (mean $Ae_{tau}\%$ values ranged between 0.696% and 1.79%) of the dose excreted in urine as unchanged drug over the dosing interval across the 30 mg - 600 mg Q8H doses. Mean CL_r values ranged between 0.293 to 0.630 L/hr.

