Every effort should be made to ensure that protocol-required tests and procedures are completed as described. However, it is anticipated that from time to time there may be circumstances outside the control of the investigator that may make it unfeasible to perform the test. In these cases, the investigator must take all steps necessary to ensure the safety and well-being of the participant. When a protocol-required test cannot be performed, the investigator will document the reason for the missed test and any corrective and preventive actions that he or she has taken to ensure that required processes are adhered to as soon as possible. The study team must be informed of these incidents in a timely manner.

If an IV catheter is utilized for blood sample collections, ECGs and vital sign assessments (pulse rate and BP) should be collected prior to the insertion of the catheter.

For samples being collected and shipped, detailed collection, processing, storage, and shipment instructions and contact information will be provided to the investigator site prior to initiation of the study.

The total blood sampling volume for individual participants in this study is approximately 415 mL. The actual collection times of blood sampling may change. Additional blood samples may be taken for safety assessments at times specified by Pfizer, provided the total volume taken during the study does not exceed 550 mL during any period of 60 consecutive days.

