8.5.3. Plasma for Analysis of Unlabeled PF-06865571 (Periods 1 and 2)

During **Periods 1 and 2**, blood samples of approximately 3 mL to provide approximately 1.2 mL of plasma for PK analysis of unlabeled PF-06865571 will be collected into appropriately labeled tubes containing K₂EDTA at times specified in the [Schedule of Activities](#).

Instructions for the collection and handling of biological samples will be provided in the laboratory manual or by the sponsor. The actual date and time (24-hour clock time) of each sample will be recorded.

The actual times may change, but the number of samples will remain the same. All efforts will be made to obtain the samples at the exact nominal time relative to dosing. Collection of samples up to and including 10 hours after dose administration that are obtained within 10% of the nominal time relative to dosing (eg, within 6 minutes of a 60-minute sample) will not be captured as a protocol deviation, as long as the exact time of the collection is noted on the source document and the CRF. Collection of samples more than 10 hours after dose administration that are obtained \leq 1 hour away from the nominal time relative to dosing will not be captured as a protocol deviation, as long as the exact time of the collection is noted on the source document and the CRF. This protocol deviation window does not apply to samples to be collected more than 10 hours after dose administration at outpatient/follow-up visits with visit windows.

Details regarding the collection, processing, storage and shipping of the blood samples will be provided in the lab manual.

Samples collected for measurement of plasma concentrations of PF-06865571 will be analyzed using a validated analytical method in compliance with applicable SOPs.

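### As the Schedule reads, no oral-analyte blood is taken between 3 h and 6 h, just after the planned Tmax, which biases oral AUC and F modestly low

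*Protocol*

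**What the plan says.** The blood-sampling part of Protocol Section 1.3 has one row for the oral analyte in both periods, "PK of PF-06865571 following oral [¹⁴ C]PF-06865571 in P1 and unlabeled PF-06865571 in P2". It is marked at 0, 0.5, 1, 2 and 3 h. The cells for 3.08, 3.17, 3.25, 3.5, 3.75 and 4 h are empty, and the next mark is at 6 h. The Period 1 rows for total radioactivity and metabolite profiling have the same gap. In Period 2 blood is drawn during that stretch, but only on the row "PK of IV infusion", which feeds the AMS assay of the labelled IV dose.

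Sections 4.1 and 6.1.1 together set the planning Tmax. The IV dose is timed to oral Tmax and is given 3 h after the oral dose. Oral dosing is fed in both periods.

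Section 2.2.2.2 gives two sets of fed medians:
- Single doses of 5 to 1500 mg: Tmax "ranged from 1.5 to 4 hours across the dose groups". The only dose tied by name to 4 h is 1000 mg.
- Repeat dosing, Days 1, 7 and 14: a median "range of 1.5 to 3.0 hours post-dose across the 30 mg - 600 mg Q8H doses".

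Protocol Section 9.4.2.1 derives AUC by the linear/log trapezoidal rule. It defines F as dose-normalised oral AUC over IV AUC, from Period 2 only. On sampling times, Section 8.5.3 says: "The actual times may change, but the number of samples will remain the same".

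**The concern.** The longest early gap in the oral grid opens at the time the design expects the peak. If 3 h is a typical Tmax, some participants will peak inside the gap. Their Tmax is then forced to 3 h or 6 h, so it may be under- or overstated, and their Cmax is missed. The trapezoid also cuts across the top of the curve.

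Oral Cmax, Tmax and AUC in Period 1 are secondary endpoints, for parent and total radioactivity. The Period 2 oral AUC is the numerator of F. The IV profile has samples at 5, 10, 15, 30, 45 and 60 minutes around its own peak, so the oral error has no matching error in the denominator to cancel it. Section 4.2 intends to read first-pass loss from F and Fa together. A low F against an unaffected Fa would overstate that loss. The error has one direction, so more participants would not average it out.

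**Working it through.** **Does the gap survive the damaged table?** The oral-minus-IV offset is 3 h in every paired column of the header, so the header is sound. Counted against it, the metabolite row falls on 0, 0.5, 3, 6, 12, 24, 36, 48, 72, 96 and 120 h. Moving the later marks one column earlier would give 4, 9, 16 and 27 h and no 24 or 48 h sample, which is implausible. That supports 6 h as the first mark after 3 h. However, the IV row starts under oral 2 h, before the infusion, and the oral row runs on past 120 h. The original table should therefore be checked. The 4 h column of the IV row is marked whether or not that row is shifted by one column.

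**Inputs.**
- From the documents: half-life 1.5 to 5.2 h (fed single dose), with 6.92 h as the longest quoted mean; the linear/log trapezoid; grid 0, 0.5, 1, 2, 3, 6, 9, 12, 16, 24, 36, 48 h.
- Assumed: one compartment, the absorption shape, and a quantification limit of 0.1% of Cmax. The documents give no concentration profile and state no bias figure to reproduce.

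**One case by hand.** Zero-order input for 4 h, half-life 1.5 h, so k = ln 2 / 1.5 = 0.4621 per h and true Tmax = 4 h. In units of plateau concentration:
- C(t) = 1 − exp(−kt) up to 4 h, so C(3) = 0.750 and C(4) = 0.8425. Then C(6) = 0.8425 × exp(−2k) = 0.3344. The true total AUC is 4.
- True area from 3 to 6 h: [1 − (0.250 − 0.1575)/0.4621] + (0.8425 − 0.3344)/0.4621 = 0.800 + 1.100 = 1.900.
- Log trapezoid from 3 to 6 h: 3 × (0.750 − 0.3344) / ln(0.750/0.3344) = 1.543.
- Shortfall in the gap: (1.900 − 1.543)/4 = 8.9%. The 0 to 3 h trapezoids lose a further (1.377 − 1.359)/4 = 0.45%. AUC is about 9.4% low.
- Observed Cmax: 0.750/0.8425 − 1 = −11.0%.

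**All cases, true Tmax 4 h, scheduled grid** (half-life 1.5 to 6.92 h, except the last row):

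| Assumed input | AUC low by | Cmax low by |
|---|---|---|
| First-order | 1.0-1.8% | 3-4% |
| 4-stage transit | 1.4-7.2% | 8-13% |
| Zero-order | 2.5-9.4% | 11-20% |
| Gamma, shape 10, half-life 1.5 h | about 12% | about 25% |

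**Other true peaks.**
- 4.5 h: AUC is 0.9% to 10.1% low for the first three shapes, and 14% low for the sharpest gamma shape with the shortest half-life. Tmax is mostly recorded as 6 h.
- 3 h: Cmax is exact. AUC is still about 1-5.5% low for first-order, transit and gamma shape 3 to 6 inputs. It is only 0.1-0.6% low for zero-order input, whose corner falls on the 3 h sample.

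**With a 4 h sample, true Tmax 4 h:** Cmax error is 0% and AUC is 0.1% to 2.7% low.

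**Effect on F.** If the IV AUC is unbiased, F falls by the same percentage as oral AUC. A true F of 0.50 would read 0.50 × 0.990 = 0.495 at the mild end, 0.50 × 0.906 = 0.453 in the hand-worked case, and 0.50 × 0.88 = 0.44 at 12%.

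**Late samples.** At the longest quoted mean half-life, 72 h is 72/6.92 = 10.4 half-lives and 120 h is 120/6.92 = 17.3.

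**The case against.** The best defence is that the grid fits the relevant data. The medians for 30 to 600 mg, which bracket the 300 mg study dose and include a first-dose day, do not exceed 3.0 h, and a sample sits at 3 h. A reader might infer from the 4 h figure that about half the men will peak at or beyond 4 h. The documents do not support that: 4 h is the top of a range of medians up to 1500 mg and is named only for 1000 mg. What remains is that medians do not bound individuals, and that AUC is somewhat low for most shapes even at a true Tmax of 3 h.

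A second defence is that the size depends on the assumed shape. This stands. A reader might take 10-12% as the expected loss in F, but it needs a late peak, a sharp peak and the shortest half-life together. Ordinary first-order input gives 1-2%.

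A third is limited consequence. No hypothesis is tested, and the primary excretion endpoint does not use oral AUC. The permeability rule is met if either F or Fa exceeds 0.85, and Fa comes from urine. A reader might infer that the permeability call is at risk, but a low F alone does not overturn it. This defence also stands, though it does not protect the secondary PK endpoints or the first-pass estimate.

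Finally, the limit "provided the total volume taken during the study does not exceed 550 mL during any period of 60 consecutive days" is attached to additional safety samples. It should not be cited as permission for new PK draws.

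**Conclusion.** The point holds as a modest design weakness, subject to confirming the table. With no oral-analyte sample between 3 h and 6 h, a participant who peaks in that window has Tmax recorded as 3 h or 6 h and Cmax understated. Oral AUC and F are biased downwards in every case examined. At a true Tmax of 4 h the loss is about 1-2% under first-order absorption and up to roughly 10-12% for a sharp peak with the shortest half-life. The range rests on assumed absorption shapes and an unbiased IV AUC. The documents do not show how many men would peak after 3 h at 300 mg, so an expected bias cannot be given. In Period 2 the gap is one of assay assignment, because blood is already drawn. Fa and the excretion endpoint are unaffected. This is a cheap improvement and does not invalidate the plan.

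**What to change.** First, check the original Schedule to confirm the gap. If it is there:

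- **Period 2:** take a 3 mL parent aliquot at the 4 h draw already scheduled for the IV analyte. Section 8.5.3 fixes the number of samples in both periods. Either amend that sentence, or exchange a late parent sample such as the 27 h mark, which follows the 24 h one by only 3 h.
- **Period 1:** move one late parent sample, for example 120 h, to 4 h before lunch. This keeps the parent count fixed. Add a 4 mL total-radioactivity aliquot at the same draw if the sponsor accepts one more sample, since Section 8.5.1 carries the same fixed-number wording.

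Cost: a Schedule and laboratory-manual edit, one more parent assay per participant in Period 2 (none if a sample is exchanged), one new Period 1 draw time, and one fewer late Period 1 parent sample. Planned blood volume rises from about 415 mL to at most 415 + 3 + 4 = 422 mL.

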3. OBJECTIVES AND ENDPOINTS

Objectives	Endpoints
Primary:	Primary:

To characterize the extent of excretion of total radioactivity in urine and feces following administration of a single oral dose of [¹⁴C]PF-06865571.To characterize the metabolic profile and identify circulating and excreted metabolites following administration of a single oral dose of [¹⁴C]PF-06865571.	
Total recovery of radioactivity in urine, feces and total excreta (urine + feces) as percentage of total radioactive dose administered.Metabolic profiling/identification and determination of relative abundance of [¹⁴C]PF-06865571 and the metabolites of [¹⁴C]PF-06865571 in plasma, urine and feces.
Secondary:	Secondary:

To quantify plasma PK parameters of PF-06865571 and total radioactivity following administration of a single oral dose of [¹⁴C]PF-06865571.To quantify plasma PK parameters of PF-06865571 following administration of a single, IV, microtracer of [¹⁴C]PF-06865571.To determine the absolute oral bioavailability (F) of PF-06865571 following administration of a single oral dose of PF-06865571 compared to a single IV microtracer of [¹⁴C]PF-06865571.To determine the fraction of the dose absorbed (Fa) following administration of a single oral dose of [¹⁴C]PF-06865571.	
Period 1: AUC_{last}, C_{max}, T_{max}, and if data permit, AUC_{inf} and t_{1/2} to describe single oral dose of:
Total radioactivity in plasmaPF-06865571 in plasma[¹⁴C]PF-06865571 (Period 2): AUC_{last}, C_{max}, T_{max}, and if data permit, t_{1/2}, AUC_{inf}, CL and V_{ss}.Plasma AUC_{inf} of oral unlabeled PF-06865571 and IV microtracer of [¹⁴C]PF-06865571 in Period 2 only.Total urinary radioactivity following oral administration of [¹⁴C]PF-06865571 in Period 1 and IV microtracer administration of [¹⁴C]PF-06865571 in Period 2.
Tertiary/Exploratory:	Tertiary/Exploratory:

To characterize cumulative rate of excretion of total radioactivity in urine and feces over time following administration of a single oral dose of [¹⁴C]PF-06865571.	
Cumulative recovery of radioactivity in urine and feces, and total excreta (urine + feces) over time as a percentage of total radioactive dose administered.

Objectives	Endpoints

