Eligible participants will be admitted to the CRU on Day -1 of Period 1 and scheduled to remain in the CRU through the completion of Period 2. As such, inpatient stay will be for a total duration of 12 days (minimum) to 25 days (maximum). Each participant will have 1 -follow-up phone call that will occur at least 28 days and up to 35 days following the last dose of investigational product to assess for AEs and SAEs.

In exceptional cases, participants may leave the CRU for personal reasons, at the discretion of the investigator, for up to a maximum of 8 hours during Period 1 after Day 7, if the participant has completed Period 1 based on the completion criteria defined in Figure 1.

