2.1. Study Design

This study is a Phase 1, open-label, non-randomized, 2-period, fixed-sequence, single-dose study of PF-06865571 in healthy male participants to characterize the ADME properties of $[^{14}\text{C}]$ PF-06865571 following oral administration; and to evaluate the absolute oral bioavailability (F) and fraction absorbed (Fa) of PF-06865571 following oral administration of unlabeled PF-06865571 and IV administration of $[^{14}\text{C}]$ PF-06865571.

In this study, 6 participants will be enrolled to ensure evaluable data is acquired in at least 4 participants. Each participant will receive 2 regimens (A and B) in Periods 1 and 2, respectively, as outlined in Figure 1. Participants who withdraw from the study may be replaced if the number of evaluable participants is less than 4.

Figure 1. Two Period Fixed Sequence Study Design

* Completion of Period 1 (1 participant at a time) when at least 1 of 3 criteria are met: (1) $\geq 90\%$ of radioactive dose has been recovered in urine+feces+emesis (if any); (2) $< 1\%$ of radioactive dose has been recovered in urine+feces during 24H interval over 2 consecutive days; (3) participant has reached Day 21 (in Period 1). At the latest, Period 2, Day -1 would occur on the same day as Period 1, Day 21.

Regimen A in Period 1: An oral dose of 300 mg PF-06865571 containing approximately 300 nCi ^{14}C (ie, radiolabeled PF-06865571).

Regimen B in Period 2: An oral dose of 300 mg unlabeled PF-06865571 followed at T_{max} by an IV dose of 300 nCi $[^{14}\text{C}]$ in 100 μg of PF-06865571 (3 $\mu\text{Ci}/\text{mg}$ active drug).

Screening will occur within 42 days of the first dose of the investigational product in Period 1. All participants will provide informed consent and undergo screening evaluations to determine their eligibility.

Eligible participants will be admitted to the CRU on Day -1 of Period 1 and scheduled to remain in the CRU through the completion of Period 2. As such, inpatient stay will be for a total duration of 12 days (minimum) to 25 days (maximum). Each participant will have 1 follow-up phone call that will occur at least 28 days and up to 35 days following the last dose of investigational product to assess for AEs and SAEs.

A participant is considered to have completed the study if he has completed all phases of the study, including the last scheduled procedure as mentioned in the Schedule of Activities in the study protocol.

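### The 90% recovery criterion can end Period 1 excreta collection while excretion still exceeds 1% of dose per day, leaving some primary recovery totals as floors of 90% or more

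*Protocol*

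**What the plan says.** Footnote c to the Schedule of Activities (Protocol 1.3) governs "Dosing in Period 2 (as 1 cohort) or Completion of Period 1 (1 participant at a time"), and any one of three criteria is enough. The first is 90% cumulative recovery: "when at least 1 of 3 criteria are met: (1) ≥90% of radioactive dose has been recovered in urine+feces+emesis (if any". The second is "2) <1% of radioactive dose has been recovered in urine+feces during 24H interval over 2 consecutive days". The third is "3) participant has reached Day 21 (in Period 1"). The Figure 1 footnote (Protocol 4.1) repeats the rule, and so does SAP 2.1: "Completion of Period 1 (1 participant at a time) when at least 1 of 3 criteria are met".

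The first primary endpoint (Protocol 3) is "Total recovery of radioactivity in urine, feces and total excreta (urine + feces) as percentage of total radioactive dose administered".

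The surrounding provisions are these:

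- Footnotes q and r schedule urine and feces in named intervals to 120 h for everyone, then in further 24 h intervals with no stated end. They also require a blank within 24 h before dosing in each period.
- Footnote a says: "There will be a wash-out period of 8-22 days from drug administration in Period 1 and Period 2". It adds that Period 2 begins only after Period 1 sample collection is complete.
- Section 4.1 has participants "scheduled to remain in the CRU through the completion of Period 2". It allows an exceptional absence of up to 8 hours after Day 7, but only for a man who has completed Period 1.
- SAP 8.2.1 lists and summarises total recovery. It has no rule for a total cut short by criterion 1 and does not ask which criterion each man met.

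**The concern.** Criterion 2 is the plan's own test that excretion has effectively ended. Criterion 1 bypasses it. If collection ends when Period 1 is completed, a man who reaches 90% after the fixed schedule has his primary endpoint stopped by its own value, and his recorded total is a lower bound. It is then summarised with totals from men followed to the <1% per day plateau or to Day 21, in a study of 6 men with as few as 4 evaluable. The cumulative excretion curve has the same cut-off. If the late tail lies mainly in one route, the urine/feces split is affected too, although the documents give nothing from which to size that.

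Early stopping does not by itself shorten the stay. Period 2 is dosed as one cohort, no sooner than 8 days after the Period 1 dose, and the men remain in the unit. Excreta not kept during that wait cannot be recovered later.

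**Working it through.** **1. Reproduce the plan's stay.** Stay = 1 day (Day -1) + days from Period 1 dose to Period 2 dose + 3 days of Period 2.

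- Minimum gap, 8 days: 1 + 8 + 3 = 12 days.
- Maximum gap, 21 days (Period 2 Day -1 on Period 1 Day 21): 1 + 21 + 3 = 25 days.

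Both match Section 4.1. The 22-day upper washout limit in footnote a would give 26, so 21 days is used here.

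**2. Time confined after the fixed schedule.** At the minimum gap, 192 − 120 = 72 h, or three 24 h intervals. At the maximum, 504 − 120 = 384 h, or sixteen.

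**3. Size of the truncation.** The documents give neither final recovery R nor the time T at which 90% is reached, so both are assumed over a range. With one-phase first-order excretion and T in days:

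- k = −ln(1 − 90/R) / T
- amount in the next 24 h = (R − 90) × (1 − e^(−k))
- shortfall = recovery when criterion 2 is met − 90

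Example, R = 100 and T = 5 (120 h): k = 2.303/5 = 0.461 per day. The next 24 h hold 10 × (1 − 0.631) = 3.69% of dose. The ninth and tenth intervals hold 0.93% and 0.58%, so criterion 2 is met at 240 h with 99.0% recovered, and the shortfall is 9.0 points.

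Each cell gives % of dose in the next 24 h / shortfall in points:

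| 90% first reached | R = 100% | R = 97% | R = 94% |
|---|---|---|---|
| 120 h | 3.69 / 9.0 | 2.86 / 6.5 | 1.87 / 3.4 |
| 144 h | 3.19 / 9.0 | 2.48 / 6.2 | 1.64 / 3.2 |
| 168 h | 2.80 / 8.6 | 2.19 / 5.9 | 1.45 / 3.0 |
| 240 h | 2.06 / 7.5 | 1.62 / 4.6 | 1.08 / 2.4 |
| 336 h | 1.52 / 5.6 | 1.20 / 3.0 | 0.81 / 1.5 |

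Only the last cell is already below the 1% limit in the next 24 h.

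**4. Early excreters.** If 90% is reached at 48 h or 72 h and the schedule still runs to 120 h, the shortfall is 0.2 or 1.9 points (R = 100), 0.1 or 1.0 (R = 97), and 0.0 or 0.3 (R = 94).

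**5. Cross-check with a separate tail.** Assume 90.5% recovered at 120 h, a tail half-life of 24-48 h and final recovery of 94%, 97% or 100%. The recorded total is 3.5, 6.5 or 9.5 points below final. The next 24 h hold from 3.5 × (1 − 2^(−24/48)) = 1.0% to 9.5 × (1 − 2^(−24/24)) = 4.8%. Collecting 120-192 h recovers from 3.5 × (1 − 2^(−72/48)) = 2.3 points to 9.5 × (1 − 2^(−72/24)) = 8.3 points. If final recovery is only 91-92%, about 1 point is lost (0.5 to 1.5).

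**6. Upper bound.** With true recovery no more than 100%, the loss cannot exceed 100 − 90 = 10 points.

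**The case against.** The strongest reply is that nothing in the text says collection stops at 90%. The criteria speak of completing Period 1 and dosing Period 2, and footnotes q and r leave the later intervals open-ended. That stands. The stop is inferred from three provisions taken together: footnote c is attached to the Day 7-21 column, footnote a makes Period 2 wait for collection to finish, and leave from the unit is allowed only after completion. If the sponsor intends collection to continue, the text does not say that either.

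Several stronger readings are tempting but unsupported:

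- A reader might infer that collection ends the moment 90% is reached, even on Day 2 or 3. It does not; everyone is scheduled to 120 h, and the criteria arguably act only from Day 7.
- A reader might infer that a completed man sits in the unit with nothing collected. Urine and feces blanks are still taken before Period 2, although these are not a recovery collection.
- A reader might infer that excretion of several percent per day is expected. The only half-life for a single fed dose is that of the parent drug, 1.5 to 5.2 h (Protocol 2.2.2.2). None is given for total radioactivity, so neither a slow nor a fast tail is documented.
- A reader might extend the problem to bioavailability. F uses Period 2 plasma and Fa uses urine to 48 h; neither is touched.

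It is also fair that a 90% stop fits the aim of near-complete collection in Section 2.3.1, that no hypothesis is tested, and that individual cumulative profiles are plotted, so a still-rising curve would be visible. Visibility does not supply the missing intervals or say how such a total should be summarised.

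**Conclusion.** The point holds as a bounded weakness in a primary endpoint and merits a cheap improvement. Criterion 1 completes Period 1 without the rate test, and on the natural but unstated reading it can end collection after 120 h while excretion exceeds 1% of dose per day. The resulting total is a floor of at least 90% (counting any emesis, as criterion 1 does). It is low by about 1.5 to 9 points if 90% is first reached at 120-336 h and final recovery is 94-100%, by under 2 points if 90% is reached by 72 h, and never by more than about 10. These figures rest on assumed one-phase kinetics and an assumed final recovery. How many of the 6 men would be affected cannot be estimated from the documents.

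**What to change.** Amend footnotes a, c, q and r of the Schedule of Activities, the Figure 1 footnote, and SAP 2.1 and 8.2.1 as follows:

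- Keep the criteria for starting Period 2 exactly as they are.
- State that, after criterion 1 is met and while the man is confined, 24 h urine and feces collection continues until less than 1% of dose is recovered in each of 2 consecutive 24 h intervals or until Period 2 Day -1, whichever is first.
- Reword footnote a so that this continued collection ends at Period 2 and does not delay it. Otherwise the two rules become circular.
- Report the primary total through the last assayed interval, and list the criterion each man met.

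The cost is wording plus assays: at the minimum washout, 3 intervals (counting Day -1) × 2 matrices × 6 men = 36. It is more if the cohort waits longer and a man has not reached the plateau. Excreta must be kept, or a gap recorded, during any exceptional 8-hour leave. No confinement, blood sampling or visits are added.

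The gain is partial where Period 2 follows soon. In the worked example, recovery by 192 h is 100 × (1 − 10^(−1.6)) = 97.5%, so 7.5 of the 9.0 points are recovered. A man whose own late completion releases the cohort may gain no interval at all, and for him the listed criterion is what tells the reader that the total is a floor.
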